Cycle/Day	Screening ¹		Treatment							EOT/ EOS ²	LTFU ³³	Extended -Use ³⁴	Extended -Use EOT/ EOS ²
			Cycle 1 (21-Days)		Cycle 2 (21-Days)		Cycle 3 (21-Days)	D1 of Every Cycle (After C3)	D1 of Every Other Cycle (After C3)				
Day	-28 to 1	-14 to 1	1	8 (±1D)	15 (±1D)	1 (±1D)	15 (±1D)	1 (±1D)	1 (±1D)	(+30D)	(±14D)	After Main EOS	(+30D)
Pregnancy Test (FSH and Estradiol, if needed) ²⁴		X	X			X		X	X	X			X
Hepatitis B and C Virus Tests ²⁵	X												
CPK (Total and MM Isoenzymes) ²⁶			X		X	X		X	X	X			
CT Scan ²⁷	X							X (±1 week)		X			
Brain MRI ²⁸	X												
RECIST v1.1 Tumor Response Assessment ²⁹								X (±1 week)		X			X
Study Treatment Administration													
RMC-4630 ³⁰			<-----	----->								X	
Sotorasib ³¹			<-----	----->								X	
Dosed QD----->													

Table 1: Schedule of Activities for Protocol RMC-4630-03 (Continued)

Cycle/Day	Screening ¹	Treatment							EOT/ EOS ²	LTFU ³³	Extended -Use EOT/ EOS ²	Extended - Use EOT/ EOS ²	
		Cycle 1 (21-Days)		Cycle 2 (21-Days)		Cycle 3 (21-Days)	D1 of Every Cycle (After C3)	D1 of Every Other Cycle (After C3)					
Day	-28 to 1	-14 to 1	1 (±1D)	8 (±1D)	15 (±1D)	1 (±1D)	15 (±1D)	1 (±1D)	1 (±1D)	(+30D)	(±14D)	After Main EOS	(+30D)
PK and Biomarker Assessment													
PK Sampling ³²			See Table 2										
Blood for ctDNA biomarker ³³			See Table 2							X			
Archival tumor tissue (FFPE) for solid tumors or fresh-tissue biopsy ³⁴	X												
Long-Term Follow-up													
Telephone contact for survival status ³			Only completed after EOT								X		

¹ Screening window is 14 days, unless otherwise specified. Informed consent and subject demographics, medical history, smoking status, documentation of tumor genotypic mutations, screening hepatitis tests, CT/MRI scan, ECHO/MUGA, and ophthalmic examination may be obtained 28 days before C1D1.

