5.1. Inclusion Criteria

All subjects must meet ALL of the following inclusion criteria to be admitted into the study:

1. Subject must be ≥ 18 years of age at the time of signing the ICF.
2. Subject is capable of giving signed informed consent, which includes compliance with the requirements and restrictions listed in the ICF and in this protocol.
3. Subject must have pathologically documented, locally advanced or metastatic $KRAS^{G12C}$ NSCLC (not amenable to curative surgery) that has progressed on prior standard therapies (**no more than 3 prior lines of therapies are allowed**), as follows:
 - a. Subject with actionable oncogenic driver mutations (eg, epidermal growth factor receptor (EGFR), anaplastic lymphoma kinase [ALK], and reactive oxygen species proto-oncogene 1 [ROS1]) must have received standard-of-care anticancer treatments, including approved drugs for oncogenic drivers in their tumor type.
 - b. Subject's tumor must harbor a $KRAS^{G12C}$ mutation assessed by a CLIA-/CAP-certified laboratory or equivalent per region.
 - c. Subjects with locally advanced $KRAS^{G12C}$ NSCLC must have received prior radio-chemotherapy followed by immunotherapy (applicable only in France)
4. Subject must have measurable disease per RECIST v1.1, criteria.
5. Subject must have a life expectancy of at least 3 months.
6. The subject's ECOG PS of 0 to 1 with no deterioration in PS at 2 weeks prior to C1D1. Rescreening is required if PS is >1 for any reason prior to C1D1.
7. Subject must have the ability to typically ingest and retain PO medications.
8. Subject must have adequate hematological and biological function, as follows:
 - a. Bone marrow function
 - i. Absolute neutrophil count (ANC) $\geq 1.5 \times 10^9/L$ without use of hematopoietic growth factors
 - ii. Hemoglobin ≥ 9 g/dL; subject must not have received a red blood cell (RBC) transfusion within 28 days of Screening
 - iii. Platelets $\geq 100 \times 10^9/L$; subject must not have received a platelet transfusion within 14 days of Screening
 - b. Subject must have hepatic function as follows:
 - i. AST and ALT $\leq 2.5 \times$ upper limit of normal (ULN)
 - ii. Bilirubin $\leq 1.5 \times$ ULN ($<2.0 \times$ ULN for subject with documented Gilbert's syndrome or $<3.0 \times$ ULN for subject for whom the indirect bilirubin level suggests an extrahepatic source of elevation)

c. Subject must have renal function as follows:

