5.2. Exclusion Criteria

If a subject meets **ANY** of the following criteria, he or she will be excluded from study participation:

1. Subject has primary central nervous system (CNS) tumor(s)
2. Subject has known or suspected leptomeningeal or brain metastases or spinal cord compression. However, subjects who were previously treated for these conditions who have had stable CNS disease (no evidence of clinical and radiographic disease progression and asymptomatic in the absence of corticosteroids or anti-convulsant

therapy) are eligible to participate in the study, as long as SD is documented by a brain magnetic resonance imaging (MRI) performed within 28 days of C1D1.

3. Subject who has any of the following cardiac abnormalities:
 - a. Medically uncontrolled hypertension (≥ 160 mmHg systolic blood pressure or ≥ 100 mm Hg diastolic blood pressure)
 - b. Congestive heart failure Class ≥ 2 , as defined by the New York Heart Association
 - c. Acute coronary syndrome (including unstable angina, coronary artery stenting, or angioplasty, bypass grafting within prior 6 months); myocardial infarction within 6 months of informed consent.
 - d. History or evidence of current, uncontrolled, clinically significant, unstable arrhythmias
 - i. Subject with medically controlled atrial fibrillation >1 month prior to Study Day 1 is eligible.
 - ii. Subject who has a pacemaker in place to control atrial arrhythmias is a candidate for the study.
 - e. History of congenital long QT syndrome or prolonged corrected QT interval (QTc) >470 msec for females and > 450 msec for males using Fridericia's formula (unless a pacemaker is in place) or uncorrectable abnormalities in serum electrolytes (ie, sodium, potassium, calcium, magnesium, phosphorus):
 - i. Subject may use average of triplicate readings for assessing QTc interval.
 - ii. Subject with an implantable defibrillator is not eligible to participate in the study.
 - f. Current cardiomyopathy or history within in the past 12 months prior to informed consent.
 - g. Baseline left ventricular ejection fraction (LVEF) below the institutional lower limit of normal (LLN) or $<50\%$, whichever is lower.
4. Any prior history of (or active) ILD or pneumonitis, or prior thoracic radiotherapy within 2 months of enrollment.

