5.4. Screen Failures

Screen failures are defined as subjects who consent to participate in the clinical study but are not subsequently able to receive treatment in the study. A minimal set of screen failure information is required to ensure transparent reporting of screen failure subjects to meet the Consolidated Standards of Reporting Trials (CONSORT) publishing requirements and to respond to queries from regulatory authorities. Minimal information includes demography, screen failure details, eligibility criteria, and any serious adverse event (SAE).

Individuals who do not meet the criteria for participation in this study (ie, screen failure) may be rescreened within 5 days of the initial screening date of screen failure. Rescreened subjects should be assigned the same subject number as for the initial screening. Only hematology, chemistry, and coagulation tests may need to be repeated if outside the screening window. Other clinical testing will not need to be repeated if outside screening window (ie, within 5 days).

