- Subjects must be informed that their participation is voluntary. Subjects will be required to sign a statement of informed consent that meets the requirements of 21 CFR 50, local regulations, ICH guidelines, Health Insurance Portability and Accountability Act (HIPAA) requirements, where applicable, and the IRB/IEC or study center.
- The medical record must include a statement that written informed consent was obtained before the subject was enrolled in the study and the date the written consent was obtained. The authorized person obtaining the informed consent must also sign the ICF.
- Per IRB/IEC requirements, subjects must be reconsented to the most current version of the ICF(s) during their participation in the study.
- A copy of the ICF(s) must be provided to the subject.

Subjects who are re-screened are not required to be re-consented; all re-screening should occur within 5 days of the initial date of the screen failure (see [Section 5.4](#))

The investigator or authorized designee will explain to each subject the objectives of the exploratory research. Any remaining mandatory samples may be used for optional exploratory research. Subjects will be told that they are free to refuse to participate and may withdraw their consent at any time and for any reason during the storage period.

Data Protection

- Subjects will be assigned a unique identifier by the Sponsor. Any subject records or datasets that are transferred to the Sponsor will contain the identifier only; subject names or any information which would make the subject identifiable will not be transferred.
- The subject must be informed that his/her personal study related data will be used by the Sponsor in accordance with local data protection law. The level of disclosure must also be explained to the subject.
- The subject must be informed that his/her medical records may be examined by Clinical Quality Assurance auditors or other authorized personnel appointed by the Sponsor, by appropriate IRB/IEC members, and by inspectors from regulatory authorities.

Dissemination of Clinical Study Data

- The posting of company Sponsored clinical trial information and tabular study results on the United States (US) National Institute of Health (NIH) website (www.clinicaltrials.gov) and on other regional clinical trial registries in countries or regions where the clinical trial is conducted, will comply with local regulations.

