or MRI can be considered measurable lesions if the soft tissue component meets the definition of measurability described above.

- Blastic bone lesions are nonmeasurable.

Cystic Lesions:

- Lesions that meet the criteria for radiographically defined simple cysts should not be considered malignant lesions (neither measurable nor nonmeasurable) since they are, by definition, simple cysts.
- Cystic lesions thought to represent cystic metastases can be considered measurable lesions if they meet the definition of measurability described above. However, if noncystic lesions are present in the same subject, these are preferred for selection as target lesions.

Lesions with Prior Local Treatment:

- Tumor lesions situated in a previously irradiated area or in an area subjected to other locoregional therapy are usually not considered measurable unless there has been demonstrated progression in the lesion. Study protocols should detail the conditions under which such lesions would be considered measurable.

Specifications by Methods of Measurements

Measurement of Lesions

All measurements should be recorded in metric notation, using calipers if clinically assessed. All baseline evaluations should be performed as close as possible to the treatment start and never more than 4 weeks before the beginning of the treatment.

Methods of Assessment

The same method of assessment and the same technique should be used to characterize each identified and reported lesion at baseline and during follow-up. Imaging based evaluation should always be done rather than clinical examination unless the lesion(s) being followed cannot be imaged but are assessable by clinical exam.

a. Clinical Lesions

Clinical lesions will only be considered measurable when they are superficial and ≥ 10 mm diameter as assessed using calipers (eg, skin nodules). For the case of skin lesions, documentation by color photography including a ruler to estimate the size of the lesion is suggested. As noted above, when lesions can be evaluated by both clinical exam and imaging, imaging evaluation should be undertaken since it is more objective and may also be reviewed at the end of the study.

b. Chest X-Ray

Chest CT is preferred over chest X-ray, particularly when progression is an important endpoint, since CT is more sensitive than X-ray, particularly in identifying new lesions. However, lesions on chest X-ray may be considered measurable if they are clearly defined and surrounded by aerated lung.

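### Protocol Section 5.4 lets a rescreened subject carry over out-of-window imaging, contradicting the 28-day limits in Appendix 6, Exclusion 2 and Table 1

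*Protocol*

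**What the plan says.** Protocol Section 5.4 allows a subject who fails screening to be tried again: such a subject "may be rescreened within 5 days of the initial screening date of screen failure". Appendix 1 (Informed Consent Process) repeats the period: "all re-screening should occur within 5 days of the initial date of the screen failure". Section 5.4 then divides the tests into two groups. For the first, "Only hematology, chemistry, and coagulation tests may need to be repeated if outside the screening window". For the second, "Other clinical testing will not need to be repeated if outside screening window (ie, within 5 days"). Neither sentence mentions tumor imaging or brain MRI.

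Four other places limit how old those assessments may be:

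- Appendix 6, Measurement of Lesions: baseline evaluations are to be close to treatment start and "never more than 4 weeks before the beginning of the treatment".
- Section 5.2, Exclusion 2: subjects with previously treated, stable CNS disease are eligible only "as long as SD is documented by a brain magnetic resonance imaging (MRI) performed within 28 days of C1D1".
- Table 1, footnote 28: the brain MRI is required within 4 weeks of C1D1 for subjects with a history or suspicion of brain metastases.
- Table 1, footnote 1: "Screening window is 14 days, unless otherwise specified", with a 28-day allowance for CT/MRI, ECHO/MUGA, hepatitis tests and the ophthalmic examination, among others.

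**The concern.** A site that uses the permission in Section 5.4 can treat a subject on a scan that Appendix 6 and Table 1 call too old, or on a brain MRI that no longer satisfies Exclusion 2. A site that keeps to those limits must set the Section 5.4 permission aside. The protocol does not say which text governs.

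Two things are at stake. The baseline sum of diameters is the reference for partial response (Appendix 6, Response Criteria), and so for the primary endpoint. Tumor growth between an old scan and first dose counts against treatment, which pushes ORR down. Separately, the MRI documenting stable CNS disease can be older than the criterion it is meant to satisfy.

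The SAP does not catch this. SAP Section 7.1 takes baseline as the last non-missing assessment before first dose, and SAP Section 5 asks only for measurable disease at baseline in the efficacy-evaluable population. Neither limits the age of the scan.

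**Working it through.** **1. Do the passages conflict?** Section 5.4 covers all testing outside its three named panels and applies it expressly to tests that are out of window. CT/MRI and brain MRI are not in those panels. Appendix 6, Exclusion 2 and footnotes 1 and 28 set 28 days (4 weeks) and provide no exception for rescreening. For a scan more than 28 days old at C1D1, Section 5.4 says no repeat is needed and the others say the scan is too old.

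**2. How large is the overrun?** Age at C1D1 = age at screen failure + delay to rescreening + time from rescreening to C1D1. Inputs are the 28-day limit and a delay of up to 5 days. Take the last term as 0, the earliest possible start.

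- Scan at the limit, 1-day delay: 28 + 1 = 29 days.
- Scan at the limit, 5-day delay: 28 + 5 = 33 days.
- Scan 24 days old, 5-day delay: 24 + 5 = 29 days, a breach.
- Scan 23 days old, 5-day delay: 23 + 5 = 28 days, no breach.

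With the full delay and an immediate start, only scans 24 to 28 days old at failure are affected. If the parenthetical is a 5-day tolerance, 33 days is the ceiling. If it merely repeats the rescreening period, Section 5.4 gives no ceiling, because it sets no maximum from rescreening to C1D1.

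**3. Which items are exposed?** Those done once in the 28-day window and not scheduled again at C1D1: CT/MRI, brain MRI, ECHO/MUGA (next due at C2D1), hepatitis serology and the ophthalmic examination where indicated.

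**4. What could this do to response?** The documents give no growth rate, so assume a tumor volume doubling time DT of 60 to 120 days. For a true 30% reduction measured from treatment start, the change read against a scan d days old is 0.7 × 2^(d / (3 × DT)) − 1.

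- d = 28, within the limit: −26.1% (DT 120) to −22.0% (DT 60).
- d = 33: −25.4% (DT 120) to −20.5% (DT 60).
- Increment from the 5 extra days: 26.1 − 25.4 = 0.7 points, to 22.0 − 20.5 = 1.5 points.

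SAP Section 2.3 expects 20 to 40 subjects at the expansion dose. One changed classification would therefore move ORR by 1/20 = 5.0 to 1/40 = 2.5 percentage points, but nothing in the documents shows that even one would change.

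**The case against.** The strongest reply is that Section 5.4 is permissive. Saying a test need not be repeated does not amend an eligibility criterion. A subject whose MRI is too old still fails Exclusion 2, Section 8 requires all eligibility criteria to be confirmed, and the Sponsor Medical Monitor reviews the eligibility documents before enrollment (Section 6.3). This stands in part and makes a breach on the brain MRI less likely. It helps less with the baseline scan: Inclusion 4 asks for measurable disease and says nothing about scan age, so the limit rests on Table 1 and Appendix 6 alone.

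It could also be said that footnote 27 allows ±7 days for CT/MRI. In Table 1 that allowance sits with the on-treatment scans, while screening is given as Day −28 to 1.

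Several stronger readings are tempting, and the documents do not support them:

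- A reader might infer that ECOG PS escapes reassessment, since Inclusion 6 says "Rescreening is required if PS is >1 for any reason prior to C1D1" and PS is not on the repeat list. Footnote 15 requires PS at C1D1 for every subject.
- A reader might add ECG, urinalysis and pregnancy test. All are scheduled again at C1D1 or within 72 hours of it (footnotes 13, 23 and 24).
- A reader might compute 28 + 5 + 14 = 47 days by opening a new 14-day window at rescreening. No text opens one; footnote 1 counts back from C1D1.
- A reader might claim that the extra days turn a true 30% shrinkage from PR into SD. On the assumptions above, a compliant 28-day-old scan already reads it as SD.
- A reader might rely on the ban on waivers in Sections 5 and 8. A rule printed in the protocol is not a waiver, so this adds little.

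**Conclusion.** The contradiction is real and the text is wrong as written: Section 5.4 cannot be applied to an out-of-window scan or brain MRI without breaching Appendix 6, Exclusion 2 or Table 1. Its severity is minor.

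The overrun is 1 to 5 days on the tolerance reading and has no stated limit on the other. The conflict exists on both. It reaches only rescreened subjects with an assessment near its limit, and for the brain MRI only those with previous or suspected brain metastases. Their number is not given and is probably small in a study of about 46 (SAP Section 2.3).

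Any bias in ORR would be downward. At 0.7 to 1.5 percentage points of tumor change per affected subject, under the assumed doubling times, the expected effect on ORR is small. A material effect is not shown.

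**What to change.** Reconcile Section 5.4 with Table 1 footnotes 1 and 28, Exclusion 2 and Appendix 6. One way is to replace its last sentence with a condition: an assessment may be carried over at rescreening only if it will still meet its own stated window (Table 1, Appendix 6, Exclusion 2) on C1D1. The parenthetical about 5 days should be removed or its meaning stated. If the sponsor does intend a tolerance, the other passages need to say so. This point takes no view on how long any window should be.

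The cost is one sentence in an amendment. The condition requires no test that the other passages do not already require.

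Protocol Version 5.0 adds an Extended-Use phase, so enrollment may be finished; the documents do not say. If it is, the deviation review before database lock (SAP Section 7.3) can list treated subjects whose baseline imaging was more than 28 days old at first dose. If there are any, ORR can be reported with and without them.

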6. STUDY TREATMENT

6.1. Study Treatments Administered: RMC-4630 and Sotorasib

The study treatment for this protocol is combination therapy of the investigational drug product RMC-4630 and the marketed product sotorasib.

RMC-4630 [REDACTED] will be administered PO on [REDACTED] of each week in a 21-day cycle (ie, Days 1, 2, 8, 9, 15, and 16 of each 21-day cycle). RMC-4630 capsules should not be crushed or chewed.

Sotorasib [REDACTED] mg will be administered PO QD per instructions provided in the current Sotorasib IB. At the Sponsor's discretion, new subjects enrolling on this trial may be treated at sotorasib 240 mg in combination with RMC-4630 (see [Table 4](#)). Subjects currently enrolled at sotorasib 960 mg may continue at their current dose or dose reduce based on discussion with the Sponsor Medical Monitor. Subjects developing toxicities at sotorasib [REDACTED] may dose reduce to sotorasib [REDACTED] or discontinue treatment.

For the main protocol, the subject should administer the study treatment at approximately the same time every day except for clinic visit days as listed in the SoA ([Table 1](#)). On these clinic visits, the subject should await instruction from the study staff to coordinate with the timing of PK and/or biomarker sampling.

Subjects deriving benefit from treatment who enter the Extended-Use phase of the study should continue treatment without interruption.

Table 4: Study Treatment Administered: RMC-4630 and Sotorasib

Component Name	Drug Product Information
Treatment Name	RMC-4630 and sotorasib combination therapy
Type	Drugs
Dose Formulation	RMC-4630: PIC drug product Sotorasib: tablet
Unit Dose Strengths	RMC-4630: [REDACTED] g Sotorasib: 120 mg
Dosage Levels	RMC-4630: [REDACTED] for a treatment cycle of 21 days Sotorasib: [REDACTED] QD
Route of Administration	PO with water after 1 hour fast; no food or drink (other than water) allowed for 1 hour after administration for RMC-4630 alone or RMC-4630 in combination with sotorasib. PO; no restrictions on food for sotorasib when taken alone.
Investigational Product	RMC-4630 in combination with Sotorasib IMP to be supplied for all sites unlabeled drug product sourced from Amgen

Table 4: Study Treatment Administered: RMC-4630 and Sotorasib (Continued)

Component Name	Drug Product Information
Sourcing	RMC-4630: Manufactured and provided centrally by the Sponsor through the third party CMO Sotorasib: IMP (unlabeled drug product supplied by Amgen) to be provided by Sponsor
Packaging and Labeling	RMC-4630: Study treatment (PIC drug products) is packaged in 8-count HDPE bottles with open label. Sotorasib: IMP (unlabeled drug product supplied by Amgen) to be provided for all sites
Current/Former Name(s) or Alias	RMC-4630, RMC-0694630 Sotorasib: AMG 510

Abbreviations: CMO = contract manufacturing organization; HDPE = high-density polyethylene; IMP = investigational medicinal product; PIC = powder-in-capsule; PO = oral(ly); QD = daily; US = United States.

6.2. Preparation/Handling/Storage/Accountability

RMC-4630 (powder in capsule [PIC] drug products: 20 mg and 100 mg, respectively) are packaged in high density-polyethylene (HDPE) bottles with open labeling and are shipped and stored below 30°C (86°F) but they are not to be frozen.

Clinical sotorasib 120 mg tablets are yellow, oblong-shaped, film-coated, debossed with “AMG” on one side and “120” on the opposite side. Sotorasib tablets are packaged in 120-count HDPE bottles.

Sotorasib is stored at 20°C to 25°C (68°F to 77°F). Excursions permitted from 15°C to 30°C (59°F to 86°F).

The sotorasib tablets supplied by Amgen will be clinically labeled and QP released as IMP and distributed to the site by the Sponsor.

The investigator or designee must confirm appropriate temperature conditions have been maintained during transit for all study treatment received and any discrepancies are reported and resolved before use of the study treatment.

Only subjects enrolled in the study may receive RMC-4630 and sotorasib as a combination and only authorized site staff may supply study treatment to the subjects.

The investigator, institution, or the head of the medical institution (where applicable) is responsible for study treatment accountability, reconciliation, and record maintenance (ie, receipt, reconciliation, and final disposition records).

Further guidance and information for the final disposition of unused study interventions are provided in the study Pharmacy and Investigational Product Administration Manual.

